6 STATISTICAL METHODOLOGY

6.1 General Considerations

Efficacy data will be summarized for each age group (children [5 to <12 years of age] and adolescents [12 to <18 years of age]) by treatment group and visit, and safety data will be summarized for each age group and overall, by treatment group and visit, unless otherwise specified.

In general, continuous data will be summarized descriptively including the number of subjects (n), mean, standard deviation (SD), median, minimum and maximum. Categorical data will be summarized by frequencies and percentages. Percentages by categories will be based on the number of subjects with no missing data, i.e. the percentages for the non-missing categories will add up to 100%.

All statistical comparisons will be conducted using 2-sided tests at the 10% significance level unless stated otherwise. All null hypotheses will be of no treatment difference, all alternative hypotheses will be two-sided, unless specifically stated otherwise.

All data summarization and analyses will be performed using SAS® Version 9.4 or higher on Red Hat Enterprise Linux. Specifications for table, figure, and data listing formats can be found in the TLF specifications.

6.2 Study Population

6.2.1 Disposition of Subjects

The following subject data will be presented, for each of the two age categories, separately, and overall:

- Number of subjects with informed consent, discontinued before randomization, randomized (overall only) (All Screened Set)
- Number and percentage of subjects randomized in each analysis set, by treatment group and overall (All Randomized Set)
- Number and percentage of subjects completed and discontinued screening, by primary reason for treatment discontinuation (including COVID-19 reasons) for randomized subjects (overall only) (All Screened Set)
- Number and percentage of subjects completed and discontinued treatment, by primary reason for treatment discontinuation (including COVID-19 reasons) for randomized subjects, by treatment group and overall (All Randomized Set)
- Number and percentage of subjects completed and discontinued the follow-up period, by primary reason for post-study period discontinuation (including COVID-19 reasons) for randomized subjects and by treatment group and overall (All Randomized Set)
- Number and percentage of subjects excluded from PPS by reason for exclusion defined in Section 4.5.1, by treatment group and overall (FAS)
- Number and percentages of subjects per protocol version (All Screened Set).

A listing of inclusion and exclusion criteria, listing of first and last evaluations as well as a listing of subjects who were excluded from at least 1 analysis set will be provided for the All Randomized Set.

6.2.2 **Protocol Deviations**

The number and percentage of subjects with the following protocol deviation criteria will be summarized for each criterion and overall, for each age group and overall, by treatment group and total as well as by investigative site. Subjects deviating from a criterion more than once will be counted once for the corresponding criterion.

The unique identifiers will be as follows:

- PD1 Entered into the study even though they did not satisfy entry criteria
- PD2 Developed withdrawal criteria during the study and was not withdrawn
- PD3 Received wrong treatment or incorrect dose
- PD4 Received excluded concomitant treatment
- PD5 Clinical study procedure conducted prior to signing the initial consent form
- PD6 Events not reported within the expected turnaround time per regulatory reporting requirements
- PD7 Missed safety or efficacy assessments related to primary or key secondary endpoints

6.2.3 Demographic and Other Baseline Characteristics

Demographic and other baseline characteristics will be summarized by descriptive statistics. Summaries will be presented, for each age group and overall, by treatment group.

Descriptive statistics for age, height (at baseline), weight (at baseline), BMI (at baseline, calculated as: weight $(kg)/(height(cm)/100)^2$), and EBC (=[age+1] × 30 in mL for children and 400 mL for adolescents) will be presented as well as frequency tabulations for sex, ethnicity, and race.

Note: for calculation of EBC the age of the subject in years [no decimals] will be used. Summaries for height and weight with respect to age- and sex-specific percentiles will be provided. This will be done using SAS code and dataset stored on the Centers for Disease Control (CDC) and Prevention website:

https://www.cdc.gov/nccdphp/dnpao/growthcharts/resources/sas.htm. These summaries will be produced for the SAF, FAS and PPS.

Number and percentage of subjects randomized to treatment in each region, country and site will be presented, for each age group and overall, by treatment group for the SAF. Geographical regions are defined as follows:

- Europe: Belgium, Denmark, France, Germany, Italy, the Netherlands, Norway, Poland, Russian Federation, Serbia, Spain, Turkey, Ukraine, United Kingdom
- Asia and Pacific (APAC): Korea (Republic of), Malaysia, Philippines

- North America: United States, Canada and Mexico
- Southern Hemisphere: South Africa

The final list of participating/enrolling countries might be updated after end of recruitment when the list becomes final. If sites in additional countries will be opened due to changes in recruitment strategy, these countries will be allocated respectively and reported in the CSR.

Medical history is coded in MedDRA, and will be summarized by System Organ Class (SOC) and Preferred Term (PT) as well as by PT alone, for each age group and overall by treatment group for the SAF.

Demographic data and other baseline characteristics will be provided in listing format by country, site and subject for the All Screened Set.

6.2.4 **Previous and Concomitant Medications**

Previous and concomitant medications are coded with WHO-DD, and will be summarized by therapeutic subgroup (ATC 2nd level) and chemical subgroup (ATC 4th level) and preferred WHO name, for each age group and overall, by treatment group for the SAF.

Subjects taking the same medication multiple times will be counted once per medication and investigational period. A medication which can be classified into several chemical and/or therapeutic subgroups is presented in all chemical and therapeutic subgroups.

Previous medications are defined as medications that patients started and ended prior to first administration of study medication. Concomitant medications are defined as any medications that subjects took after the first dose of study medication and through Follow-up period (EoS). Medications that started prior to first administration of study drug and continued while study drug was given will be counted in both previous and concomitant medications.

Previous and concomitant medication data as well as non-medication therapy data will be provided in listing format by country, site and subject for the All Screened Set.

6.3 Study Drug Exposure and Compliance

6.3.1 Exposure

The following information on drug exposure will be presented, for each age group and overall category, by treatment group for the SAF:

- Descriptive statistics for cumulative amount of the drug to which the subject was exposed; and
- Number and percent of subjects with dose increases, decreases or interruptions.

Duration of exposure will be summarized in two ways.

- Descriptive statistics will be presented by age category and treatment group.
- Exposure time will be categorized according to the following categories by age category and treatment group:
 - less than 14 days
 - at least 14 days, less than 28 days
 - at least 28 days, less than 56 days

- 56 days or more
- Unknown.

Counts and percentages of subjects in each of these categories will be summarized, for each age group and overall, by treatment group for the SAF.

Exposure details will be provided in listing format by country, site and subject for the All Randomized Set.

6.3.2 Treatment Compliance

Overall compliance with the dosing schedule will be examined for subjects in the SAF whose total study drug count and first and last days of treatment are known.

Percent overall compliance will be summarized in two ways for the SAF:

- Descriptive statistics will be presented, for each age group and overall, by treatment group.
- Percent compliance will be categorized according to the following categories, for each age group and overall, by treatment group:
 - less than 70%
 - at least 70%, less than 80%
 - at least 80%, less than 120%
 - at least 120%, less than 130%
 - greater or equal than 130%
 - Unknown.

Treatment compliance details, including all data relevant to the calculation, will be listed by country, site and subject for the All Randomized Set.

6.4 Analysis of Efficacy

Efficacy analysis of the data from children (5 to <12 years of age) will be conducted on the FAS and PPS, and interpretation of results from statistical tests will be based on the FAS. The PPS will be used to assess the robustness of the results from the statistical tests based on the FAS.

Efficacy analysis in adolescents (12 to <18 years of age) will only be exploratory, and will be conducted on the FAS.

No multiplicity adjustment will be necessary in this study.

Efficacy data will be summarized for each age group by treatment and visit (week 2, 4, 8 and 12/EoT) unless otherwise specified. Efficacy data will be provided in listing format by country, site and subject for the All Randomized Set.

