3 SAMPLE SIZE

Efficacy of mirabegron in children will be based on both primary and secondary endpoints. Given the clinical hurdle to demonstrate efficacy in a population challenging to recruit, an alpha-level of 10% would appear reasonable and justified. In a study with propiverine in children, Marschall-Kehrel (2009) showed a difference in mean number of micturition episodes/24 hours of 0.8 between propiverine and placebo, with a standard deviation (SD) between 2.2 and 2.3. Assuming at least similar efficacy of mirabegron, with a treatment effect of 0.9 micturitions per day between mirabegron and placebo and a common SD of 2.3, a sample size of 82 evaluable subjects (children) per treatment group would provide a power of 80%.

These assumptions, together with levels for Type-1 error and power were agreed upon with Pediatric Committee in the current Pediatric Investigation Plan.

Under the assumption that after randomization about 10% of the subjects will not be evaluable for the analysis of the primary endpoint (i.e., not fulfilling the criteria for inclusion in FAS), at least 184 children (5 to < 12 years of age) must be randomized in order to have at least 164 evaluable children for the analysis of the primary efficacy endpoint. For adolescents, no formal sample size will be calculated, at least 32 adolescents (12 to <18 years of age) must be randomized, yielding at least 16 adolescents on mirabegron.

Further assuming a 50% screen failure rate, approximately 368 children have to be enrolled to achieve 184 children (5 to <12 years of age) randomized and approximately 64 adolescents will be enrolled to achieve at least 32 adolescents (12 to <18 years of age) randomized (at least 92 children and 16 adolescents must be randomized to mirabegron).

Recruitment will continue until the minimum number in both children and adolescents has been achieved.

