6.4.1.1 Primary Analysis for Primary Efficacy Endpoint

The primary estimator for the primary estimand as defined in Section [2.1.1 Estimand] will be calculated according to the evaluation of the primary efficacy endpoint. The primary efficacy endpoint will be analyzed using an analysis of covariance (ANCOVA). The ANCOVA model will include treatment group, sex and geographical region as fixed effects and the mean number of micturitions per 24 hours at baseline as covariate. This analysis will be performed with imputation of missing visit 7/week 12 data using the last observation carried forward (LOCF) method.

The hypothesis for comparisons is given as follows:

- H₀: The adjusted mean change from baseline at visit 7/week 12 in mean number of micturitions per 24 hours for mirabegron and placebo are the same.
- H1: The adjusted mean change from baseline at visit 7/week 12 in mean number of micturitions per 24 hours for mirabegron and placebo are not the same.

Statistical testing will be done 2-sided at a 10% significance level. A 90% CI for the treatment difference (mirabegron – placebo) will be provided. The primary analysis will use the FAS. The plausibility of the underlying assumption of missing at random for the primary estimator will be evaluated and, therefore, the estimation of the treatment effect.

The ANCOVA model results will be presented with least squares (LS) means and two-sided 90% confidence intervals (CIs) for mean changes from baseline within each treatment group. Differences in LS means between mirabegron versus placebo will be derived and presented together with two-sided 90% CIs. T-statistics corresponding to the Type III sums of squares for the differences in the LS means will be used to obtain p-values for the comparisons.

Model fitting will be visually assessed. A scatter plot of residuals versus predicted values, along with histogram and normal probability plots will be produced.

Sensitivity analyses under alternative assumptions for missing data mechanisms such as missing not at random to show robustness of the estimates will be further specified.

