6.4.2 Analysis of Secondary Efficacy Endpoints

Descriptive statistics (n, mean, SD, minimum, median, maximum) and the same primary efficacy analysis (ANCOVA) as for the primary endpoint will be applied to change from baseline at the end of the 12-week treatment period in children (5 to <12 years of age) for:

- Mean volume voided per 24 hours
- Maximum volume voided
- Mean number of daytime incontinence episodes per 24 hours
- Mean number of daytime micturitions per 24 hours

Change from baseline in the number of dry (incontinence free) days per 7 days at the end of the 12-week treatment period will be analyzed with a negative binomial regression model including treatment group, sex, geographical region as factors and the log baseline rate of number of dry days (e.g., the log of the ratio of dry days and number of diary days at baseline) as covariate.

Data of these secondary efficacy endpoints will be analyzed both without imputation and with imputation using the LOCF method, for the FAS.

The same analysis detailed in Section 6.4.1.3 will be performed for all the secondary efficacy endpoints on the FAS as sensitivity analysis.

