6.9 Interim Analysis (and Early Discontinuation of the Clinical Study)

One comparative interim analysis will be performed after 50% of children planned to be randomized have had their week 12/EoT assessment. Only data from those children with week 12/EoT assessment will be used in the interim analyses. The interim analysis will determine if the chance of a positive study with respect to the primary endpoint at the final analysis is high enough to justify continuation of the study; otherwise, the study will be stopped for futility.

Given the data at the interim analysis, a predictive probability of a positive study will be calculated. A positive study is defined as the final 1-sided p-value ≤ 0.05 when comparing mirabegron vs. placebo in the primary efficacy analysis (in children [5 to < 12 years of age]).

If the predictive probability is $\leq 5\%$ at this interim evaluation, the study will be recommended to stop for futility. Otherwise, the study will continue.

No efficacy analyses will be performed except for determination of futility.

At the interim analysis, the following predictive probability will be calculated: Predictive Probability of ({final one-sided p-value of mirabegron vs. placebo ≤ 0.05 } |Data).

Since we use non-informative prior distribution of difference in mean change from Baseline to week 12/EoT in mean number of micturitions per 24 hours between the mirabegron group and the placebo group and assume the mean change from Baseline to week 12/EoT in mean number of micturitions per 24 hours follows a Gaussian distribution, the Bayesian predictive probability for the event of a final one-sided p-value of mirabegron vs. placebo ≤ 0.05 (denoted by *PP*) can be obtained using a closed form based on the methods described in Geisser and Johnson (1994), Spiegelhalter etc. (2004), Dmitrienko and Wang (2006). Appendix 9.5 contains a detailed derivation.

$$PP = \Phi \left\{ \sqrt{\frac{2}{\frac{M_P}{N_P} + \frac{M_A}{N_A}}} \left[\sqrt{82} \frac{\overline{y}_{N_P} - \overline{x}_{N_A}}{\sqrt{2}\hat{\sigma}} - z_{0.95} \right] \right\}$$
(1)

where

- Φ stands for the cumulative distribution function for the standard Gaussian distribution. $\Phi(Z_{0.95}) = 0.95$.
- N_P and N_A denote the number of subjects observed at the interim analysis for placebo group and mirabegron group, respectively.

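### The statement that no multiplicity adjustment is needed holds only if the primary endpoint alone decides efficacy, but the plan also bases efficacy on the secondary endpoints, each tested at the full two-sided 10%

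*SAP*

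**What the plan says.** - **Basis for efficacy.** SAP 3: "Efficacy of mirabegron in children will be based on both primary and secondary endpoints". Protocol 9.1 and the synopsis carry the same sentence.
- **Level.** SAP 6.1: "All statistical comparisons will be conducted using 2-sided tests at the 10% significance level unless stated otherwise". SAP 6.4.1.1 sets the primary test at that level too: "Statistical testing will be done 2-sided at a 10% significance level".
- **Secondary tests.** For mean volume voided, maximum volume voided, daytime incontinence and daytime micturitions, SAP 6.4.2 says that "the same primary efficacy analysis (ANCOVA) as for the primary endpoint will be applied". Dry days get a negative binomial regression. That makes five secondary tests, and no other level is stated for them.
- **Multiplicity.** SAP 6.4: "No multiplicity adjustment will be necessary in this study". It gives no reason, testing order or split of alpha.
- **Positive study.** SAP 6.9 and protocol 9.10 define it as a one-sided p-value of 0.05 or less "when comparing mirabegron vs. placebo in the primary efficacy analysis". The definition serves the futility rule.

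**The concern.** The plan gives two bases for concluding efficacy: the primary test alone (SAP 6.9, protocol 9.10), or the primary together with the secondaries (SAP 3, protocol 9.1, synopsis). They can give different answers when the primary misses and a secondary reaches p < 0.10. SAP 6.4 fits only the first basis.

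If the second basis is used so that any one of six endpoints can carry the conclusion, nothing in the plan limits the error across the set, and the level per test is already 10% two-sided. Settling the question after unblinding would look driven by the data.

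**Working it through.** **1. The plan's own figure.** Inputs from SAP 3: difference 0.9, SD 2.3, two-sided alpha 10%, power 80%.

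n per arm = 2 × (1.645 + 0.842)² × 2.3² / 0.9² = 80.8, so 81. At the planned 82 per arm, power is 80.5% (80.2% by the noncentral t). Allowing for 10% non-evaluable, 82 / 0.9 = 91.1, so 92 per arm and 184 in total. The sample size reproduces, and it concerns the primary endpoint only. The 5.0% false-positive rate in the futility simulation (SAP Appendix 9.4) also concerns the primary test only.

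**2. Number of tests.** One primary plus the five secondaries of SAP 6.4.2 gives six. Nighttime incontinence is still listed in SAP 5.2 and protocol 9.4.2 but has no analysis in SAP 6.4.2, so it is left out. Each endpoint is counted once, although SAP 6.4.2 analyses the secondaries both with and without LOCF.

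**3. Independent endpoints, all six nulls true.**
- Any false rejection, either direction: 1 − 0.90⁶ = 1 − 0.531 = 46.9%.
- Any false rejection in favour of mirabegron (5% per test): 1 − 0.95⁶ = 1 − 0.735 = 26.5%.

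**4. Correlated endpoints.** The documents give no correlation, so it is varied. The test statistics are Z_j = √ρ·S + √(1−ρ)·E_j, with S and E_j independent standard normal; 1,000,000 draws; critical value 1.645.

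| Assumed common correlation | Any false rejection, either direction | Any false rejection in favour of mirabegron |
|---|---|---|
| 0 | 46.9% | 26.5% |
| 0.3 | 42.9% | 22.1% |
| 0.5 | 37.0% | 18.6% |
| 0.7 | 29.5% | 14.8% |
| 0.8 | 25.1% | 12.6% |
| Primary alone | 10% | 5% |

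**5. A gate alone is not enough for claims on secondaries.** If the primary effect is real and no secondary effect is, the five secondaries at full level give at least one false rejection with probability 33% at correlation 0.5 (41% at 0, 23% at 0.8) in either direction, and 17% (23% to 12%) in favour of mirabegron.

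**The case against.** The case for leaving the sentence alone has several parts.

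- **Most of the plan makes the primary decisive.** There is one primary endpoint, one formal pair of hypotheses, an estimand on micturition frequency only, sizing on that endpoint only, and a positive study defined on it. Endpoints are ranked as primary, secondary and exploratory, and the exploratory tier includes children. This stands, and for the primary test the SAP 6.4 sentence is correct. But the ranking is not a testing order, and nothing calls the secondaries supportive.
- **A win on any endpoint is not a written rule.** A reader might infer that one secondary at p < 0.10 suffices after a failed primary. No section says so. The SAP 3 sentence can also be read as requiring success on both kinds of endpoint; the false-positive rate then cannot exceed that of the primary. This stands: the inflation belongs to one reading. The text does not choose between the readings.
- **The upper bounds are unlikely.** Daytime micturitions are part of 24-hour micturitions, both volume endpoints use the same recorded volumes, and dry days and daytime incontinence both come from leakage reports. Assuming correlations of 0.8 to 0.9 within those three pairs and 0.3 to 0.5 otherwise, the same simulation gives about 31% to 37% in either direction and 15% to 19% in favour of mirabegron. This stands against the zero-correlation figures, but the rates remain about three times those of the primary alone.
- **The 10% level was agreed.** SAP 3 and protocol 9.1 record agreement with the Pediatric Committee on the assumptions, the Type-1 error level and power. The level is therefore not at issue here. The recorded agreement does not mention several endpoints.

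**Conclusion.** The point holds as an unresolved conflict between two stated bases for efficacy. SAP 6.4 fits one of them and not the other.

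The primary test's error stays at 10% two-sided, and the futility-only interim does not inflate it. If a secondary can support efficacy when the primary misses, the chance of at least one false result in favour of mirabegron is about 13% to 27%, against 5%. This assumes six tests, all nulls true and a common correlation between 0 and 0.8.

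A reader might infer that the trial has a 37% chance of a false efficacy result where it promises 10%. The documents do not support that. The 37% counts results favouring placebo as well and needs an assumed correlation of 0.5. The 10% is a level per test, and no family-wise rate is stated anywhere.

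**What to change.** In SAP 6.4, replace the sentence with: *The study is positive only if the primary analysis (6.4.1.1) is significant at two-sided 10%; the secondary endpoints in 6.4.2 are supportive, with nominal p-values, and cannot by themselves establish efficacy.* Align the sentence on the basis for efficacy in SAP 3, protocol 9.1 and the synopsis.

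If claims on secondaries are wanted, test them only after a significant primary, with Holm's procedure or a prespecified fixed sequence at an overall two-sided 10% across the five endpoints. Name which of the two versions, with or without LOCF, carries the test. Under Holm the smallest secondary p-value must be at most 0.10 / 5 = 0.02.

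Neither option changes the sample size, the primary test or its power. By contrast, Bonferroni over all six (0.10 / 6 per test) would cut primary power at 82 per arm to 54% and need 137 per arm for 80%.

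The cost is wording. SAP section 1 allows revisions before hard lock, and the protocol sentence can change at the next amendment. The one loss is that a lone secondary at p < 0.10 can no longer be presented as efficacy.
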